5.0 Study Procedures

5.1 Study Design

Experimental Design

This mixed-methods study will utilize qualitative and quantitative methods to achieve its three primary aims. The present study will occur at two HCV clinics located at the VAPAHCS and SFVAMC. Our study sites were chosen out of concerns for cost (e.g., VA is under a tight

research funding cap) and study coordination concerns (e.g., less resources needed to manage study sites with close locations). Obviously, no two clinics in the VA system can fully represent all the realities of care and patients nationally, but it is possible to document carefully the characteristics of the selected clinics so that contextual features that may affect generalizability are known. Accordingly, we will measure both site specific and general characteristics that can be used to inform the research questions posed by each study aim. Specifically, data gathered from qualitative interviews will inform the initial implementation and re-versioning of a web-based BAI for use at both study sites. We will then use a randomized, hybrid (type 1) design with patient level clinical outcome data and formative evaluation data collected to examine the effectiveness of the web-based BAI (Curran et al., 2008) at both sites.

“Hybrid designs” integrate formative evaluation into experimental designs to identify factors that impact the effectiveness of implementation efforts (Stetler et al., 2008). Formative evaluation will be conducted and consist of site visits, clinic observations, and provider interviews to identify potential and actual influences on the progress and effectiveness of the initial implementation efforts that may impact the likelihood that the web-based BAI will be adopted at both sites.

Finally, a budget impact analysis will estimate the costs of adoption and diffusion of the BAI for Veterans with HCV and the trajectory of health care spending for these patients. We will estimate the budgetary impact from the VA’s perspective using a one year time horizon, without discounting. We will use costs of the intervention and the subsequent health spending for participants during their enrollment in the study (six-months) and six-months after enrollment for a total of one year.

Aim 1 (Year 1)

To address Aim 1, we will conduct qualitative semi-structured interviews with Veterans and clinic staff at both sites to achieve two objectives: (a) identify patient, provider, and system factors that serve as potential facilitators or barriers to the initial adoption of a web-based BAI as an intervention for reducing alcohol consumption, and (b) obtain patient and provider feedback on the content and presentation of a web-based BAI to help inform its redesign for use with Veterans with HCV and consuming any level of alcohol. Re-versioning the existing intervention will increase its usefulness and adoptability among HCV providers and patients with HCV by enhancing its relevance to the specific health needs of this population. Interviews with providers and patients will be conducted over the phone.

Risks and Benefits

There are no anticipated risks associated with participation in Aim 1 of this study. However, interviews may involve risks that are currently unforeseeable. For example, it is possible that participants may experience some discomfort answering some of the questions. The benefits which may reasonably be expected to result from this study include providing the scientific community with information on HCV care and the utility of BAI in HCV clinics.

Study Population

Study coordinators at both sites will conduct semi-structured (audio-recorded) interviews, over the telephone, with both patient (N = 30, 15 per site) and provider (N=10, 5 per site) participants to help inform both the initial implementation and the re-versioning of the web-based BAI for two VA HCV clinics. Patients will include men and women veterans who have been diagnosed with HCV, attend the HCV clinic at VAPAHCS or SFVAMC, and are currently using any level of alcohol. Patients with evidence of active psychosis, dementia, and/or terminal illness will be ineligible to participate. Providers from HCV clinics at VAPAHCS or SFVAMC will be eligible to participate.

Aim 2 (Years 2-3)

Our second aim is to implement a re-versioned web-based BAI in two liver clinics and to evaluate the implementability and effectiveness of this intervention to reduce alcohol consumption in Veterans with liver disorders at three- and six-months post treatment. To achieve Aim 2, we will conduct a randomized controlled trial utilizing a hybrid (Type 1) design with patient-level clinical outcome data and formative evaluation data collected (Curran et al., 2008). Participants will be randomized to one of two treatment conditions –(a) web-based BAI plus treatment-as-usual (TAU) or (b) TAU only. We will also conduct a formative evaluation to determine the feasibility and challenges of implementing the web-based BAI into liver clinics.

Method for Randomization

We plan to use a stratified permuted block design for randomizing participants where participants are stratified by site (Palo Alto or San Francisco) and baseline severity of alcohol use (alcohol dependent, not alcohol dependent). Four randomization strata will be used: not alcohol dependent (Palo Alto), alcohol dependent (Palo Alto), not alcohol dependent (San Francisco), and alcohol dependent (San Francisco). Within each stratum, we will construct blocks of consecutive patients that vary randomly in size (either 8 or 12 participants). Each block will contain equal quantities of assignments to the two study arms arranged (permuted) in random order. A random mixture of block sizes of 8 and 12 will be used to prevent forecasting

of treatment assignments by project personnel since neither the participants nor the project staff will not be blinded to the assigned treatment condition.

Web-Based BAI Content

Participants in the experimental condition will receive a web-based BAI which follows the general approach that has proven to be effective in previous studies. The BAI consists of two components (a) a brief computerized assessment and (b) a personalized feedback report. The domains that are assessed in the BAI, and on which Veterans received personalized feedback are: (a) typical alcohol consumption; (b) lifetime negative consequences of alcohol use; (c) risk factors for unsafe drinking (e.g., combat experience, history of sexual assault, using drugs/alcohol to cope with symptoms of PTSD); (d) past 90 day use of illicit drugs, and (e) willingness to change alcohol use. Assessment information is entered into the BAI computer program directly by the patient. Our prior work demonstrated that the assessment portion of the BAI takes approximately 10-20 minutes to complete.

Once patients complete the assessment portion of the BAI, an individualized feedback report is generated for them to print out and review on their own. A study coordinator will be responsible for guiding participants through the study protocol including making sure patients print out the feedback report and answering any patient questions that might arise. The personalized feedback report was developed using the principles of motivational interviewing and consists of the following elements – a summary report of patients' weekly use of alcohol and/or other substances; normative feedback on their alcohol use with respect to their age-matched peers; estimates of the consequences of their alcohol use on their health, finances, and time spent "under the influence"; a chart indicating their peak blood alcohol content (BAC) on a day within the past 90 days when they drank the most; psychoeducation on the physiological effects of various BAC values and factors that increase/decrease BAC; social consequences of alcohol and other substance use; any reported risk factors for increasing the social/health consequences of using alcohol; and a summary of their self-reported motivation to change their alcohol consumption.

Treatment-as-Usual (TAU)

TAU in this study consists of brief education (delivered face-to-face) about the health effects of alcohol consumption on HCV disease progression (e.g., fibrosis, cirrhosis, viral load). When indicated, education is delivered by a liver clinic provider (e.g., physician assistants and mental health providers) and typically takes 5-15 minutes. This is the most commonly delivered form of TAU at both clinics. At the discretion of the assessing provider, Veterans may be encouraged to seek further assessment and treatment depending on the severity of alcohol use (e.g., abuse or dependence). These services might consist of educational classes and outpatient mental health. Participation in these services is not considered TAU and will be measured at each follow-up assessment.

Formative Evaluation Plan

We will utilize a well-established formative evaluation protocol that will include two site visits (to each study site) and interviews with staff (at each site) at three-month post initial implementation (e.g., Curran et al., 2008). This protocol will help our team identify potential and actual influences on the progress and effectiveness of the initial implementation efforts that may impact the likelihood that the web-based BAI will be implemented and sustained at both sites.

The formative evaluation will consist of two site visits in which the research team will conduct observations that will focus on clinic policies, norms, and staff-patient relationships (especially related to screening and treating current alcohol use and use of the web-based BAI).

Observations will be both formal and informal. The former will consist of “scheduled” observations where the study coordinators will observe intake interviews, screening efforts for alcohol use, educational presentations, and referral of patients reporting current alcohol use to the web-based BAI. Study staff will also perform informal observations of patient flow, and staff and staff-patient relationships in central clinic locations (e.g., nurses’ station). The primary objective of these site visits is to generate written, revised summaries of clinic flow, processes for utilizing the web-based BAI, and recommendations for improving the sustained adoption of this intervention based on information collected through observations and interviews.

Risks and Benefits

There are minimal anticipated risks associated with participation in Aim 2 of this study. At the discretion of the assessing provider, Veterans indicating active alcohol consumption are most often provided education within the clinic setting about the harmful effects of alcohol on liver disorders. Therefore, the receipt of education is considered TAU in this proposed pilot study. In addition to receiving education, it is up to the discretion of the provider to recommend further assessment and treatment for the Veteran indicating active alcohol use. The decision for referral is based on the Veteran’s willingness and interest in further assessment and treatment and severity of alcohol use gathered while meeting with the patient. For example, at the San Francisco liver clinic, providers may recommend patients contact outpatient mental health or seek out an educational class (e.g., one-hour educational course titled “Rethinking Drinking”).

Participants randomized to the experimental condition (BAI plus TAU) will then complete the web-based BAI. They will also be asked to print out an individualized feedback report and review the report on their own (see Personalized Feedback Report sample in Appendix A). Participants randomized to the TAU only condition will complete the assessment battery and be provided a Patient Resource Sheet containing Human Subjects approved VA (e.g., Toll Free Hotline to the VA Palo Alto’s Addiction Consultation and Treatment) and non-VA resources (e.g., website to Alcoholics Anonymous meeting schedule). All Veterans participating in this study will receive the Patient Resource Sheet to help encourage them to seek additional assessment and treatment.

In the event that a Veteran participant verbally expresses interest in seeking additional care to our study staff, we will arrange additional meetings between the Veteran and his/her HCV clinic provider to discuss additional treatment options. Since our team is co-located (located within the same clinic as the liver clinic providers administering the brief education), we can help facilitate this meeting in a number of ways including walking the patient back to the provider office and/or contacting the provider while the patient is completing the study to suggest further assessment and intervention. It will also be explained (by our staff) to the participant that they may (should they choose) share the contents of their individualized feedback report with any provider.

Study Population

In collaboration with our co-investigators at each study site, [name] (Director, VAPAHCS HCV clinic) and [name] (Director, SFVAMC HCV clinic), Veterans (N = 340) diagnosed with liver disease and currently consuming any level of alcohol will be recruited to participate. Drs. [name] and [name] provided estimates of patient flow through each clinic per year and estimates of the percentage of patients reporting any level of alcohol consumption during their visit. Based on these estimates, we anticipate a sufficiently large patient pool from which we may recruit eligible participants. We also estimate, based on national VHA patient demographic data, that approximately 2-5% of clinic patients will be women. We will over sample for women patients in both study clinics utilizing expertise (in recruiting women for research studies) of the Practice Based Research Network (PBRN) based

at Palo Alto (under the leadership of [name], also a consultant) and San Francisco. This will increase our ability to conduct at least exploratory, hypothesis generating sub group analysis in women.

The study sample will be drawn from a population of Veterans who currently receive VA liver clinic services. Veterans presenting to liver clinics who report engaging in any level of alcohol use within the prior 30 days will be recruited for the study. Additional criteria for inclusion include: (a) a liver disorder diagnosis, (b) not presently in treatment for a substance use disorder, and (c) no evidence of active psychosis, dementia, and/or terminal illness. The study will be conducted in liver clinics located at the VAPAHCS and SFVAMC. We estimate that we will need 170 individuals per condition at baseline for a total sample of 340 across both sites, with one half in the experimental condition and TAU condition at each site (i.e., n=85 per condition at Palo Alto, n=85 per condition at San Francisco).

For the formative evaluation, study staff will also perform informal observations of patient flow, and staff and staff-patient relationships in central clinic locations (e.g., nurses' station). Secondly, we will conduct interviews with 10 clinic staff members (5 at each study site) that help us identify possible barriers and facilitators to the sustained adoption of the web-based BAI at both study clinics. The study coordinators will conduct these interviews with providers (N = 10) following the same general recruitment and interview approach as outlined for Aim 1.

Aim 3 (Year 4)

To achieve Aim 3, the budget impact analysis will estimate the costs of adoption and diffusion of the web-based BAI for Veterans with HCV and the trajectory of health care spending for these patients. We will estimate the budgetary impact from the VA's perspective using a one year time horizon, without discounting (Mauskopf et al., 2007). We will estimate the costs of the intervention and the subsequent health spending for participants during their enrollment in the study (six months) and 6 months after enrollment for a total of 1 year. We hypothesize that the BAI intervention will increase utilization of SUD treatment in the first 6 months and then budget neutral from 6-12 months. Savings, if any, would accrue in the 6-12 months after randomization.

With consent, the study will collect the patient's social security number. We will link the social security number to the VA scrambled social security number so that we can extract their VA utilization and cost data. We will collect utilization and cost data from randomization through one year for each participant. Data will be gathered from a variety of sources.

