4.0 Resources and Personnel

This four year study will be based at two sites - the (a) VA Palo Alto Health Care System, VA HSR&D Center for Health Care Evaluation and Liver Clinic, and (b) San Francisco VA Medical Center, Liver Clinic. This study will also collaborate with the VA Women's Health Practice-Based Research Network to provide technical expertise relevant to

administrative functions (e.g., Central IRB) and enhance our team's ability to oversample for women and optimize retention of women participants in our study.

The PI, VAPAHCS and SFVAMC Co-I's, and study coordinators from each site will have access to protected health information. De-identified information will be utilized when possible in data analysis. Study coordinators at both sites, will be involved in **recruiting** subjects and obtaining **informed consent** for Aims 1 and 2 of the study. For Aim 1, study coordinators at both sites will **administer the interviews** with patients and providers. For Aim 2, the study coordinators at VAPAHCS and SFVAMC will **administer** the web-based BAI to Veterans randomized to the treatment condition at baseline, along with the assessment survey to all Veteran participants at baseline (in-person interview), and 3- and 6-months post-treatment (phone interview). **Data analysis** will be performed by the PI and Co-Is, and supported by the consultants and research staff as detailed below.

[name]., Principal Investigator

[name] will oversee all aspects of the proposed project in partnership with our partners, The VA Office of Mental Health Services, Office of Mental Health Operations (10N), and VA Office of Public Health. He will supervise study personnel; coordinate data collection protocols, staff training, develop study procedures; and take responsibility for data analysis and the dissemination of findings. He will also co-lead development of the qualitative interviews and protocol, and participate in conducting interviews with staff and patients. He will ensure that the study protocol and all human subjects and data security regulations are followed. Dr.

[name] will also be responsible for communicating and supporting our partners in interpreting the policy and health care implications of our study findings.

[name].; Co-Principal Investigator – not VA Palo Alto

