(c) Patient satisfaction. We will use a brief patient survey that we developed from our preliminary work to assess patients' satisfaction with both treatment conditions. This survey will ask patients to respond to a series of statements regarding their satisfaction with the interventions received (e.g., "I felt comfortable disclosing my alcohol use to a computer program"; "My provider helped me understand how alcohol use may worsen liver disorder(s)."). This assessment will be completed by patients upon completion of the baseline assessment (and upon completion of the web-based BAI for patients assigned to the experimental condition).

Primary Outcomes.

(d) Alcohol quantity and frequency. Reduction in alcohol use will be measured using the 30-day Time Line Follow-Back instrument (TLFB; Sobell & Sobell, 1992). The TLFB is a calendar that provides visual cues to aid persons in retrospective recall of drinking behavior. It uses "cues" (e.g., holidays, birthdays) to help a participant recall drinking behavior (e.g., frequency and quantity of alcohol use) and has been shown to be reliable and accurate when administered individually over the telephone (Sobell et al., 1996). Based on recommendations from the alcohol treatment literature we will assess the *(a) number of drinking days, (b) mean number of drinks per drinking day, and (c) percentage of heavy drinking days* in the prior 30 days as our primary outcomes (Dieperink et al., 2010; Gastfriend et al., 2007). These outcomes will be measured by comparing TLFB drinking data at baseline (30-days prior) to data collected at three- and six-month follow-up (30 days prior).

Secondary Outcomes.

(e) Consequences of alcohol use. The Short Index of Problems (SIP-3months) is a brief, 15-item version of the Drinker Inventory of Consequences (DrInC) which assesses alcohol-related problems over the prior 3-months (Woolard et al., 2004). The SIP has sound psychometric properties (Kenna et al., 2005).

(f) Symptoms of psychological distress. Symptoms of psychological distress will be measured using the Brief Symptoms Inventory (BSI). The BSI instrument provides an overview of a patient's symptoms and their intensity at a specific point in time (Derogatis & Melisaratos, 1983). The reliability, validity, and clinical utility of the BSI instrument are well-established.

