After the interviews and transcriptions are complete, the study coordinator and [name] will begin developing two separate codebooks for patient and providers. Codebook development will be an iterative process. Codebooks will be initially developed based on close readings of 30% of patient (n = 9) and 40% (n = 4) of provider transcripts. Themes that emerge from the patient and provider interviews will be continuously integrated into their respective codebooks. We anticipate that the final set of themes will consist of both themes defined a priori and new themes that emerge from each set of interviews. Upon completion of the initial version of the codebooks, the study coordinator and [name] will discuss the application of the codebooks to each set of interviews. This process will involve practicing applying the codebooks to a single patient and provider interview. When agreement is reached, the study coordinator and [name] will code a random sample of 20% of patient (n = 6) and 20% of provider (n =2) interviews to establish inter rater reliability. Once reliability is established (80% agreement), we will proceed to code the remaining portion of the patient and provider transcripts. Throughout the coding process, the PI and [name] will regularly discuss emerging themes, changing conceptualizations of existing themes, and to prevent drift. They will also consult intermittently with the other Co-Is and consultants to discuss emerging themes and conceptualizations. After data coding is complete, data analysis will begin, focusing on the frequency of code occurrence (by participant and code) and patterns of code co-occurrence for each set of interviews.

Aim 2

Based on findings from prior studies of web-based BAIs with similar follow-up time

frames, we expect an average effect size of .35 to .40 (range is .15 to .67) on alcohol consumption outcomes in response to the web-based BAI (Kypri et al., 2004; Kypri et al., 2008; Neighbors et al., 2004). Assuming a power of 80% of detecting an effect size of .35, an alpha level of .05, a 2-tailed test, a correlation of .5 between repeated measures of an outcome variable, and a 20% attrition rate at 6 months, we estimate that we will need 170 individuals per condition at baseline for a total sample of 340 across both sites, with one half in the experimental condition and TAU condition at each site (i.e., n=85 per condition at Palo Alto, n=85 per condition at San Francisco).

Data Analysis

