Prior studies show that the effectiveness of web-based BAIs is at least partly due to the correction of misperceptions about normative alcohol use (i.e., social norms; Borsari & Carey, 2001; Neighbors et al., 2004). Therefore, we will test whether changes in social norms (e.g., descriptive and injunctive norms) mediate the effect of the web-based BAI on alcohol consumption. Following the recommendation of Baron and Kenny (1986), we will conduct a series of analytic steps (using regression models) to determine mediation: (a) we will test the effect of both intervention conditions on alcohol consumption; (b) the effect of intervention conditions on social norms; (c) the effect of social norms on alcohol consumption controlling for intervention condition; and (d) the effect of intervention condition on alcohol consumption after controlling for social norms. In addition, we will examine potential moderators (e.g., severity of alcohol use, coping, psychological distress) that may impact the effectiveness of intervention condition on treatment outcome. This analysis will help us determine whether the effectiveness of the intervention(s) is impacted by these variables at baseline and over the course of each follow-up.

Missing Data Prevention, Detection, and Adjustment

We will make every effort to prevent missing data at each assessment by achieving as high a response rate as possible. Baseline data will be collected during an in-person interview and follow-up assessments will be conducted as telephone interviews by study site

coordinators who have been trained to cover all questions and obtain as complete data as possible while respecting the patient's right to not answer specific questions. Based on previous follow-up studies of SUD patients conducted at our Center, we do not expect rates of missing data on any one variable to be greater than 5% at each assessment over and above missing data due to attrition, nor do we expect missing data to be systematically related to certain outcome variables. Nevertheless, given our plan to use an intent-to-treat approach that includes all patients who are randomized in our GLMM regression models, we will use multiple imputation. Multiple imputation procedure yields more efficient, accurate, and reliable inferences than ad-hoc methods of handling missing data (such as list wise deletion or mean substitution) (Shafer, 1997 Shafer et al., 2002; Little & Rubin, 2002).

Formative Evaluation Data Analysis

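### Unblinded site coordinators support the web-based BAI and also take the follow-up drinking interviews; exchanging the calls between the two sites would mask the interviewer at low cost

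*Combined protocol and SAP*

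**What the plan says.** - **Blinding.** Section 5.1 (Method for Randomization) explains the random mix of block sizes by the fact that "neither the participants nor the project staff will not be blinded to the assigned treatment condition". The double negative is a slip. The explanation makes sense only if staff know the arm.
- **Delivery.** Under Aim 2 in section 4.0, "the study coordinators at VAPAHCS and SFVAMC will" administer the BAI at baseline to those randomized to it. Section 5.1 (Web-Based BAI Content) adds: "A study coordinator will be responsible for guiding participants through the study protocol including making sure patients print out the feedback report". The coordinator also answers patients' questions.
- **Assessment.** The same sentence of section 4.0 gives the coordinators the outcome assessments, "along with the assessment survey to all Veteran participants at baseline (in-person interview), and 3- and 6-months post-treatment (phone interview"). Section 5.6 (Missing Data) repeats that "follow-up assessments will be conducted as telephone interviews by study site" coordinators.
- **Outcome.** Section 5.5: "Reduction in alcohol use will be measured using the 30-day Time Line Follow-Back instrument". Number of drinking days, mean drinks per drinking day and percentage of heavy drinking days all come from it.
- **Site structure.** Planned enrolment is equal ("n=85 per condition at Palo Alto, n=85 per condition at San Francisco"), and "study coordinators from each site will have access to protected health information".

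The text available describes no masked interviewer, no separation of delivery from assessment and no objective or collateral check on drinking. It does not say that masking the interviewer was considered or was infeasible.

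**The concern.** The TLFB is a cued recall interview, so the interviewer's prompting is part of the measurement. If the caller knows the arm, expectation can affect how hard a drinking day is probed or how an uncertain answer is recorded. Sections 2.0 and 3.0 say openly that the team expects the BAI to work. All three primary outcomes pass through this one interview, so none of them can serve as a check on another.

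The analysis cannot repair this. The model in section 5.6 has fixed terms for time, time by condition, and site. A shift that arises at follow-up in one arm falls into the time-by-condition term, which is the treatment effect being tested. This assumes that the baseline TLFB is recorded before the arm is known, which the text does not state outright. Multiple imputation addresses missing values, not shifted ones.

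**Working it through.** **The plan's own figure.** Section 5.6 gives 170 per condition from 80% power, effect size 0.35, two-sided alpha 0.05, correlation 0.5 and 20% attrition.

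- With correlation 0.5 the change score has SD sqrt(2(1 − 0.5)) = 1, so change and single-time comparisons need the same number.
- n = 2(1.960 + 0.842)² / 0.35² = 128.1, so 129 per arm; 129 / 0.8 = 161.3, so 162. A t-based calculation gives 130, then 163.
- The stated 170 is therefore not reproduced exactly. It is a little generous: 170 × 0.8 = 136 completers per arm give power of about 0.82. The concern does not depend on this difference.

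**Sensitivity to a reporting shift.** The shift b is an assumption, because the documents give no value. The calculation is a simple two-group comparison at one time point, not the planned repeated-measures model.

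- SE of a standardized difference = sqrt(2/136) = 0.121.
- False-positive rate with no true effect = P(Z > 1.96 − b/SE) + P(Z < −1.96 − b/SE).
- If the shift instead works against the BAI, power for a true 0.35 is that for an apparent difference of 0.35 − b.

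| Assumed shift b (SD) | Share of planned 0.35 | b/SE | Two-sided false-positive rate | Power if the shift opposes the BAI |
|---|---|---|---|---|
| 0 | 0% | 0 | 0.050 | 0.823 |
| 0.05 | 14% | 0.41 | 0.070 | 0.696 |
| 0.10 | 29% | 0.82 | 0.131 | 0.540 |
| 0.15 | 43% | 1.24 | 0.236 | 0.378 |
| 0.20 | 57% | 1.65 | 0.378 | 0.235 |

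The false-positive rate is the same whichever way the shift goes, because the test is two-sided.

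**Call load.** Each site plans 2 × 85 = 170 participants. Two calls each make 340 calls per site and 680 in total before attrition. A full exchange leaves these numbers unchanged. Randomization is stratified by site, so each caller would still interview both arms in equal planned numbers.

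**The case against.** - **The coordinator's part in the BAI is small.** Patients enter their own data, the program generates the feedback, and patients review it on their own (section 5.1). A reader might infer that patients are interviewed by the person who gave them the feedback. The documents do not support that. What stands is that the coordinator is present, answers questions and knows the arm.
- **A role is not an individual.** A reader might infer that whoever enrolled a patient also makes that patient's calls. Sections 4.0 and 5.6 name only a role. Part of the personnel section is not in the text available, so the number of coordinators and their division of work cannot be checked. Since project staff are unblinded, the caller may know the arm in either case.
- **Direction is not settled.** It is tempting to say that the bias must favour the BAI. Detailed feedback on consumption could also lead BAI patients to report more fully.
- **There are partial safeguards.** Section 5.5 describes the TLFB as a calendar method that is reliable and accurate by telephone, and section 5.6 says callers are trained. These limit interviewer discretion but do not replace masking.
- **The exchange has conditions.** Section 8.0 has the coordinators in continuous contact, and section 6.1 relies on local licensed clinical staff when a safety concern arises. The section 4.0 statement on protected health information does not say in terms that a coordinator may use the other site's records. These points add work but do not prevent the change.
- **The gain is partial.** Participants know their arm and can reveal it, and their own tendency to please remains.

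**Conclusion.** The concern holds as a design weakness that can be reduced cheaply. Unblinded site coordinators, as a role, both support delivery of the BAI and conduct the interviews behind all three primary outcomes. Nothing described would detect or remove an interviewer effect.

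Its size is unknown. The figures of 7% to 38% show how sensitive the conclusion would be to assumed shifts of 0.05 to 0.20 SD. They are not estimates of what will happen, and they attribute the whole shift to the interviewer.

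A reader might also infer that the exchange certainly needs no extra staff. That is an inference from telephone follow-up, coordinators at both sites and equal planned enrolment. Unequal actual accrual would move some of the load.

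**What to change.** For the 3- and 6-month TLFB interviews:

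1. Have the other site's coordinator, who is not told the arm, make the calls from lists and tracking files that omit the arm.
2. State that arm assignment is excluded from the cross-site communication in section 8.0.
3. Ask the TLFB before any item that could reveal the arm. Sections 5.1 and 5.5 have treatment exposure asked at follow-up. Section 5.5 also lists satisfaction in the assessment given at all time points, while its satisfaction paragraph places it at baseline; settle which applies.
4. Ask participants at the start of the call not to mention their arm, and record any unmasking.
5. Document how the caller reaches the participant's local licensed clinical staff under the existing procedure in section 6.1.
6. Confirm that consent and data-access approvals cover contact by the other site.

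The cost is a change of procedure, revised tracking files, possibly a line in the consent form, cross-site scheduling and some loss of rapport. Sample size and power are unchanged. The report should still say that participants were unblinded and that their own reporting bias remains.
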